### 2.2 Secondary Objectives:

#### Phase I

- 2.21 To evaluate the safety profile of this regimen in relapsed MM patients.

#### Phase II

- 2.22 To evaluate the progression free survival (PFS) of the combination of ibrutinib, lenalidomide, and dexamethasone in MM patients
- 2.23 To evaluate the safety profile of this regimen in untreated MM patients.
- 2.24 To evaluate the duration of response for patients treated with this 3-drug regimen.
- 2.25 To evaluate overall survival (OS) for patients treated with this 3-drug regimen

### 2.3 Exploratory Objective:

- 2.31 To explore compliance to treatment.
- 2.32 To assess effects of treatment on patient-reported quality of life (QoL) measures

### 2.4 Correlative Research Objective:

- 2.41 To determine the role of members of the BTK signalosome in achievement or lack thereof of response to ibrutinib.
- 2.42 To explore biologic effects of ibrutinib on microenvironment in MM and correlate with response to treatment.
- 2.43 To evaluate pharmacodynamic measures including receptor occupancy for BTK prior to introducing lenalidomide in patients treated with ibrutinib and dexamethasone.
- 2.44 To evaluate the impact of ibrutinib on platelet aggregation.

### 3.0 Patient Eligibility

**Phase I only: Prior to discussing protocol entry with the patient, call the MCCC Registration Office [contact]) for dose level and to insure that a place on the protocol is open to the patient.**

#### 3.1 Inclusion Criteria

3.11 Age  $\geq$ 18 years.

3.12 Diagnosis:

3.121 Phase I: Confirmed diagnosis of relapsed or refractory multiple myeloma

3.122 Phase II: Confirmed diagnosis of active multiple myeloma and must be newly diagnosed.

**NOTE:** All tests for establishing disease status must be completed  $\leq$ 28 days prior to registration.

3.13 Measurable disease  $\leq$ 28 days prior to registration, defined by at least one of the following:

- Serum monoclonal protein  $\geq$ 1.0 g/dL (see Section 11.1 for definition)
- $>200$  mg of monoclonal protein in the urine on 24-hour electrophoresis
- Serum immunoglobulin free light chain  $>10$  mg/dL AND abnormal serum immunoglobulin kappa to lambda free light chain ratio.
- Monoclonal bone marrow plasmacytosis  $>30\%$  (evaluable disease).

3.14 Prior treatment:

3.141 Phase I: Exposure to 2-3 prior lines of therapy or no therapeutic options

3.142 Phase II: Previously untreated for symptomatic MM.

**EXCEPTION:**  $\leq$ 7 days with pulse steroids or localized radiation therapy, without curative intent, for a myeloma-related complication prior to registration is allowed, as considered necessary by the treating physician.

3.15 Myeloma Frailty Score:

**NOTE:** This will include calculating a frailty score [[Appendix I](#); based on age, activities of daily living, instrumental activities of daily living ([Appendix II](#)) and Charlson comorbidity index ([Appendix III](#))].

3.151 Phase I: “Intermediate fitness” or “Frail”

**NOTE:** No “fit” patients will be included in the phase 1 portion of the trial which is being done to determine the MTD of the 3-drug combination.

3.152 Phase II: Transplant-ineligible as per their treating physician.

**NOTE:** All the patients with “intermediate fitness” or “frail” status will be considered transplant-ineligible. Other reasons to consider transplant ineligibility may include, but are not limited to: financial constraints or patient preference. In case such patients have a frailty score of “fit”, it should be duly noted by the treating physician.

3.16 ECOG Performance Status 0, 1, or 2 ([Appendix IV](#)).

3.17 The following laboratory values obtained  $\leq$ 14 days prior to registration:

- Absolute neutrophil count (ANC)  $\geq$ 1,000 cell/mm^3 without growth factor support
- Platelets  $\geq$ 50,000 cells/mm^3 for patients who have bone marrow plasmacytosis  $<$ 50% or  $\geq$ 30,000 cells/mm^3 for patients who have bone marrow plasmacytosis of  $\geq$ 50%
- Calculated or measured creatinine clearance  $\geq$ 30 ml/min (see Appendix V)
- Total bilirubin  $\leq$ 1.5 x upper limit of normal (ULN) unless due to Gilbert's syndrome.
- Aspartate aminotransferase (AST)/SGOT and alanine aminotransferase (ALT)/SGPT  $\leq$ 3 x ULN
- PT/INR  $\leq$ 1.5 X ULN

3.18 Provide informed written consent.

3.19a Willing to return to enrolling institution for follow-up (during the Active Monitoring Phase of the study).

3.19b Persons able to become pregnant must be willing to adhere to the scheduled pregnancy testing as required in the REVLIMID REMS™ program.

3.19c Willing to be registered into the mandatory REVLIMID REMS™ program, and willing and able to comply with the requirements of the REVLIMID REMS™ program.

3.19d Ability to complete study-related (QoL, pill diary) questionnaire(s) by themselves or with assistance.

3.19e Willing to provide bone marrow aspirate and core, and blood samples for correlative research purposes (see Sections 6.31, 14.0).

## 3.2 Exclusion Criteria

3.21 Non-secretory MM or known AL amyloidosis.

3.22 Clinically significant active infection requiring intravenous antibiotics  $\leq$ 14 days prior to registration.

3.23  $\geq$ Grade 3 neuropathy and/or POEMS syndrome (plasma cell dyscrasia with polyneuropathy, organomegaly, endocrinopathy, monoclonal protein, and skin changes).

3.24 Other prior malignancy.

**EXCEPTIONS:**

- Adequately treated basal cell or squamous cell skin cancer
- Any *in situ* cancer
- Adequately treated Stage I or II cancer from which the patient is currently in complete remission, or
- Any other cancer from which the patient has been disease-free for  $\geq$ at least three years prior to registration

3.25 Concurrent therapy considered to be investigational.

**NOTE:** Patients must not be planning to receive any radiation therapy (except localized radiation for palliative care that must be completed prior to starting Cycle 1, Day 1).

3.26 Any of the following because this study involves an investigational agent whose genotoxic, mutagenic and teratogenic effects on the developing fetus and newborn are unknown:

- Pregnant women
- Nursing women (lactating females are eligible provided that they agree not to breast feed while taking lenalidomide)
- Men or women of childbearing potential who are unwilling to employ adequate contraception

3.27 Requires treatment with a strong cytochrome (CYP) 3A4/5 inhibitor (as outlined in Appendix X).

3.28 Major surgery  $\leq$ 4 weeks prior to registration.

3.29a History of stroke/intracranial hemorrhage  $\leq$ 6 months prior to registration.

3.29b Requires use of therapeutic anticoagulation prior to registration  
**NOTE:** thromboprophylaxis with any agent is permitted.

3.29c History of clinically significant bleeding or known platelet or coagulation disorder.

3.29d Clinically significant cardiac illness including New York Heart Association (NYHA) Class III or Class IV heart failure (Appendix VI), unstable angina pectoris, myocardial infarction within the past 6 months, or  $\geq$ Grade 3 cardiac arrhythmias noted  $\leq$ 14 days prior to registration.

3.29e Hepatic impairment

3.29e1 Phase I  
Any currently active, clinically significant hepatic impairment (Child-Pugh class A, B, or C according to the Child Pugh classification see Appendix XII).

3.29e2 Phase II  
Currently active, clinically significant hepatic impairment Child-Pugh class B or C according to the Child Pugh classification (see Appendix XII).

3.29f Known HIV+ patients  
EXCEPTION: If they meet the following additional criteria  $\leq$ 28 days prior to registration:

- CD4 cells  $\geq$ 500/mm^3
- Viral load of <50 copies HIV mRNA/mm^3 if on cART or <10,000 copies HIV mRNA if not on cART
- No zidovudine or stavudine as part of cART

3.29g Known Hepatitis B or Hepatitis C infection  
EXCEPTION: If viral load <800,000 IU/L.

3.29h Phase I : Active dermatologic disease  $\geq$  Grade 3.

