##### Cycles 25 and beyond

Agent	Dose Level	Route	Day		Cycles
Lenalidomide	25 mg	PO	1-21	Repeat every 28 days x 3 for each cycle	Cycles 25 and beyond
Dexamethasone	40 mg*	PO	1, 8, 15, 22		

Cycle length = 84 days

\*Starting dose level of dexamethasone for patients  $\geq 75$  years old will be 20mg

Treatment schedule will follow the study schema outlined above. All patients will start with ibrutinib as assigned by the registration office, lenalidomide 25 mg PO days 1-21, and dexamethasone 40 mg PO weekly. **EXCEPTION:** Lenalidomide will be adjusted per guidelines for renal dysfunction with CrCl between 30-60 ml/min (see Table 8.32).

Treatment will be continued until disease progression as long as the patient continues to respond and does not have any unacceptable toxicity. All the patients enrolled in the trial will have a follow up for at least 3 years after registration to capture the secondary endpoints of the study.

Note: Thromboprophylaxis is required as standard of care (see Section 9.3).

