## Additional Adverse Events:

\*\* If ibrutinib is omitted in the middle of the cycle and the toxicity resolves, patient can re-start the drug but the days of drug treatment missed do not need to be caught-up and can be omitted in order to maintain the cycle schedule.

- Dose omission: Ibrutinib may be omitted for adverse event considerations for a maximum of 28 consecutive days. Study medication should be discontinued permanently in the event of AE lasting more than 28 days.
- If multiple adverse events are seen, administer dose based on the greatest reduction required by any single adverse event observed.
- Dose modifications are for adverse events attributed to study treatment only. Dose modifications are not required for adverse events if they are deemed unrelated and/or unlikely related to study treatment.

- Reductions apply to treatment given in the preceding cycle and are based on adverse events observed since the prior dose.

\*\*\*\* If cough, dyspnea, and other pulmonary symptoms occur, a chest x-ray and high-resolution chest CT scan should be obtained. Incentive spirometry studies (to include DLCO) should be considered. Consider Pneumocystis pneumonia or viral pneumonitis. Patients who experience a deep vein thrombosis (DVT), pulmonary embolus (PE), or other clotting event should have all study drugs temporarily omitted while full-dose anticoagulation is initiated (other than warfarin or other Vitamin K antagonist). There should not be a delay of more than 28 days in reinitiating the study treatment.

**NOTE:** If the patient experiences a significant adverse event requiring a dose reduction at the start of the next cycle, then the dose will remain lowered for that entire remaining length of the study treatment.

**NOTE:** Adverse events requiring a dose-reduction step for any or all drugs beyond the two dose-reduction steps (levels –1 and –2) (per Table 8.2) will be at the discretion of the treating physician, if the decision is made for the patient to be kept on study. These dose reductions must be clearly recorded in reported clinical data.

**NOTE:** For a dose omission of ibrutinib or lenalidomide of more than 28 days beyond the scheduled date of retreatment, the patient should discontinue protocol treatment and go to the event monitoring phase per Section 4.2. In the event patient is benefitting from treatment and the delay was unrelated to treatment toxicity, patient may remain on study with approval of study PI.

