### 9.3 Thromboprophylaxis

Due to the increased risk of deep vein thrombosis (DVT) for multiple myeloma patients, thromboprophylaxis is to be used as standard of care on this regimen according to the International Myeloma Working Group guidelines (<http://jco.ascopubs.org/content/32/6/587.full>).

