No dose adjustment is required in combination with mild inhibitors. Monitor patient closely for toxicity and follow dose modification guidance as needed. Avoid grapefruit and Seville oranges during ibrutinib treatment as these contain moderate inhibitors of CYP3A.

Administration of ibrutinib with strong inducers of CYP3A decreases ibrutinib plasma concentrations by up to 90%. Avoid concomitant use of strong CYP3A inducers (eg, carbamazepine, rifampin, phenytoin and St. John's Wort). Consider alternative agents with less CYP3A induction.

To minimize the potential for an interaction in the GI tract, narrow therapeutic range P-gp or BCRP substrates such as digoxin or methotrexate should be taken at least 6 hours before or after ibrutinib. Ibrutinib may also inhibit BCRP systemically and increase the exposure of drugs that undergo BCRP-mediated hepatic efflux, such as rosuvastatin.

There have been reports of bleeding-related events in subjects treated with ibrutinib. Warfarin or other vitamin K antagonists should not be administered concomitantly with ibrutinib unless specified in the protocol. Supplements such as fish oil and vitamin E preparations should be avoided.

Based on preliminary data from the combination studies of ibrutinib and venetoclax, venetoclax exposure (area under the concentration-time curve [AUC]) at 400 mg QD appears to be approximately 1.7 to 1.8-fold higher with 420 mg ibrutinib and approximately 3-fold higher with 560 mg compared with venetoclax single agent exposure. To date, no new safety signals have been identified in these ongoing combination therapy studies. Patients should be closely monitored for signs of toxicity.

Evaluation of the effect of repeated administration of ibrutinib on the PK of oral contraceptives (OC), showed that the maximal daily dose of 560 mg did not lead to a decreased exposure of OC drugs ethinylestradiol(EE)/levonorgestrel in female subjects, suggesting that the OCs remain efficacious when used during ibrutinib therapy.

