- Rarely patients can experience secondary skin cancers. Instruct patients to report any new skin lesions to the study team.

- Rash can be seen. Instruct patient to report to study team.
- Cardiac arrhythmias have been seen with this agent including a-fib, atrial flutter and ventricular tachyarrhythmia's, some of which have led to death. Instruct patients who experience any palpitations, lightheadedness, syncope, or SOB to see medical care immediately. This is especially important in patients who have pre-existing cardiac issues.
- Warn patients of the risk of bleeding. Patients should not take warfarin or other vitamin K antagonists while on ibrutinib, unless the protocol allows for it. Additionally, patients should be cautioned to avoid fish oil and vitamin E supplements.
- Patients who are concurrently on ibrutinib and ventoclax should be monitored closely for excess toxicity.
- Ibrutinib should be held at least 3-7 days pre and post-surgery, depending on type of surgery.
- There have been reports of CVA and TIA in patients on ibrutinib. Instruct patients to report any headaches and/or neurologic changes immediately or seek out emergency care.
- Patients may experience dry eyes, blurred vision or decreases in vision. Instruct patients to report this to the study team.

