### **Antiplatelet Agents and Anticoagulants**

Warfarin or vitamin K antagonists should not be administered concomitantly with ibrutinib. Supplements such as fish oil and vitamin E preparations should be avoided. Use ibrutinib with caution in subjects requiring other anticoagulants or medications that inhibit platelet function. Subjects with congenital bleeding diathesis have not been studied. For guidance on ibrutinib and the use of anticoagulants during procedures/surgeries see Section X.

Subjects requiring the initiation of therapeutic anticoagulation therapy (eg, atrial fibrillation), consider the risks and benefits of continuing ibrutinib treatment. If therapeutic anticoagulation is clinically indicated, treatment with ibrutinib should be held and not be restarted until the subject is clinically stable and has no signs of bleeding. Subjects should be observed closely for signs and symptoms of bleeding. No dose reduction is required when study drug is restarted.

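### The 3.29b note allows any thromboprophylaxis agent, 15.19b bars vitamin K antagonists with ibrutinib, and no section says which governs

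*Combined protocol and SAP*

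**What the plan says.** Criterion 3.29b excludes a patient who "Requires use of therapeutic anticoagulation prior to registration". Its note then adds that "thromboprophylaxis with any agent is permitted".

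Prophylaxis is expected on study. Section 9.3 states that "thromboprophylaxis is to be used as standard of care on this regimen according to the International Myeloma Working Group guidelines", and a note under the Phase I schedule in 7.11 also requires it. Neither place names an agent or rules one out.

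The rules on vitamin K antagonists sit elsewhere:

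- 15.16: "Warfarin or other vitamin K antagonists should not be administered concomitantly with ibrutinib unless specified in the protocol".
- 15.19a (nursing guidelines): "Patients should not take warfarin or other vitamin K antagonists while on ibrutinib, unless the protocol allows for it".
- 15.19b (antiplatelet agents and anticoagulants): "Warfarin or vitamin K antagonists should not be administered concomitantly with ibrutinib".
- 8.5 (notes after the ibrutinib table): full-dose anticoagulation after a clotting event is to be with an agent "other than warfarin or other Vitamin K antagonist".

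**The concern.** The eligibility note is open as to agent, and one treatment rule closes off a class of agents. Two other treatment rules make the closure depend on what the protocol allows, without saying where to look. A site that takes the 3.29b note as the allowance will keep a patient on warfarin. A site that reads 15.19b will not. Both are following the text.

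Section 15.16 introduces the bar by citing bleeding reports with ibrutinib, and 10.8.1 makes major hemorrhage an event of special interest. It is therefore a safety rule, and sites should not be able to reach opposite answers on it.

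**Working it through.** No arithmetic is involved. The check sets the provisions side by side and follows one patient through them.

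| Section | What it governs | Vitamin K antagonists |
|---|---|---|
| 3.29b note | Eligibility | Not excepted; any agent accepted |
| 3.17 | Laboratory eligibility, within 14 days before registration | PT/INR at most 1.5 x ULN; no drug named |
| 9.3 | Prophylaxis on the regimen | Not mentioned; refers to an outside guideline |
| 9.5 | Prohibited medications | Not listed |
| Appendix X | List that footnote j of the 4.1 test schedule uses for medication review | Not listed; covers CYP3A inhibitors and inducers only |
| 8.5 notes | Full-dose anticoagulation after a clotting event | Excluded |
| 15.16, 15.19a | Use with ibrutinib | Barred unless the protocol provides otherwise |
| 15.19b | Use with ibrutinib | Barred, no exception |

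Take a candidate already on warfarin as prophylaxis, with every other criterion met.

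1. **3.29b.** The use is prophylactic, so the exclusion does not apply, and the note accepts the agent.
2. **3.17.** The candidate passes if PT/INR is at or below 1.5 x ULN. The documents give no relation between warfarin dose and INR, so it is an assumption that some such patients fall under the limit. Those above it are already excluded.
3. **Start of treatment.** Sections 7.11 and 7.12 schedule ibrutinib on days 1-28 of each 28-day cycle from Cycle 1. Through Cycle 24 that leaves 28 - 28 = 0 scheduled days per cycle without ibrutinib, so there is no planned window in which warfarin would not be concomitant.
4. **Applying Section 15.** If the 3.29b note counts as the allowance in 15.16 and 15.19a, warfarin may continue under those two sections but still breaches 15.19b. If the note does not count, warfarin must not continue under any of the three. In that case no section tells the site to switch the agent before Cycle 1 or to decline the patient.
5. **Prophylaxis started after registration.** The 3.17 limit is a screening value and does not govern this. Section 9.3 does, and the agents its cited guideline recommends cannot be seen from the documents.

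The direct conflict is thus between the 3.29b note and 15.19b. A second inconsistency lies within Section 15, where the same bar is conditional in two places and unconditional in a third.

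**The case against.** The best defence is that the provisions apply at different moments. Criterion 3.29b concerns the time before registration, and its note only says that prophylaxis does not trigger the exclusion. The rules in Section 15 govern what may be taken with ibrutinib. A patient can be eligible and still have to change a medicine before starting. Several instructions also lead a site toward Section 15: 9.9a refers there and to the prescribing information, footnote j in 4.1 requires a medication review before every cycle, and 15.19a tells nurses to avoid the agents listed in 15.16. On this view the conditional phrases default to the bar, and a general note naming no drug is a weak basis for lifting it.

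Much of this stands. It shows that a careful site could find the Section 15 rule. It does not settle the matter, for three reasons. The note speaks of what is permitted and sets no time limit of its own. The conditional phrases invite the reader to look elsewhere in the protocol for permission. And the change of agent that the defence relies on is nowhere stated.

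Three stronger readings are tempting and are not supported:

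- A reader might infer that such a patient is eligible but cannot be treated. That is so only while the patient stays on the vitamin K antagonist. Nothing requires that, and a change before Cycle 1 would avoid the breach.
- A reader might take the whole planned enrollment as affected, because prophylaxis is general. The planned 63 (24 + 34 + 5) includes 5 allowed for ineligibility, cancellation, violations and the like, and the documents do not say how many patients would be on a vitamin K antagonist.
- A reader might infer that mixed practice distorts the dose-limiting toxicity or hemorrhage findings. A bleed in a small cohort could matter, but a dose-limiting toxicity must occur in Cycle 1 and be at least possibly attributed to study treatment (7.32), and the documents offer no count from which to show a distortion.

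**Conclusion.** The inconsistency is real and is confined to wording. The 3.29b note and 15.19b give different answers for a vitamin K antagonist used as prophylaxis, 15.16 and 15.19a leave room for either, and 9.3, 9.5 and Appendix X do not resolve it.

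Its reach is limited to patients on prophylactic vitamin K antagonists who also satisfy the PT/INR limit, and to any who start such an agent on study. That number is not given, is probably small and could be zero. The conclusion assumes only that some patient on prophylactic warfarin can meet the 3.17 limit. No statistical operating characteristic changes: sample size, alpha and power are unaffected. The case for correcting it is that sites should not reach opposite answers on a bleeding-safety rule when a short edit would prevent it.

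**What to change.** Write one explicit statement on whether vitamin K antagonists are allowed as thromboprophylaxis during ibrutinib, and reconcile 3.29b, the notes in 8.5, 9.3, 9.5, 15.16, 15.19a and 15.19b with it. In particular:

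- Replace the open wording about agents in the 3.29b note so that it says whether this class is included.
- Point 9.3, and the conditional phrases in 15.16 and 15.19a, to the single statement.
- If a candidate would have to change agent before Cycle 1, say so where eligibility and prophylaxis are described.

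Which rule applies is for the sponsor's clinicians to decide; this point takes no position on it.

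The cost is an amendment to wording, with no change to the design or analysis. If the bar is kept, a few candidates would have to change agent or would not be enrolled.

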##### Cycles 25 and beyond

Agent	Dose Level	Route	Day		Cycles
Lenalidomide	25 mg	PO	1-21	Repeat every 28 days x 3 for each cycle	Cycles 25 and beyond
Dexamethasone	40 mg*	PO	1, 8, 15, 22		

Cycle length = 84 days

\*Starting dose level of dexamethasone for patients  $\geq 75$  years old will be 20mg

Treatment schedule will follow the study schema outlined above. All patients will start with ibrutinib at the dose level determined by the phase I portion and dexamethasone 40 mg PO weekly. Lenalidomide 25 mg PO Days 1-21 will be added Cycle 2.

Treatment will be continued until disease progression as long as the patient continues to respond and does not have any unacceptable toxicity. All the patients enrolled in the trial will have a follow up for at least 3 years after registration to capture the secondary endpoints of the study.

7.2 Treatment by a local medical doctor (LMD) is not allowed.

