**ALERT:** **ADR reporting may be required for some adverse events (See Section 10)**

#### 8.1 General Considerations:

- a) Missed doses are to be omitted rather than made up, unless the dose of one of the study drugs was forgotten and remembered on the same day, in which case the dose can be taken that day. Any doses missed on a particular day are not to be made up the next day.

Doses that are considered to be vomited are not to be made up and a mention about the time of dose and time of vomiting episode should be made in the pill diary.

- b) If multiple toxicities are experienced, dose modifications will be based on the toxicity requiring the largest dose reduction.
- c) Reductions are based on the dose given in the preceding cycle and are based on toxicities with an attribution of possible, probable, or definite that were observed since the prior toxicity evaluation.
- d) If either ibrutinib or lenalidomide must be permanently discontinued, the patient will be removed from the protocol therapy.
- e) If a drug is omitted due to specific adverse events and the patient is on combination therapy, the other agents, considered unrelated to the adverse event may be continued.
- f) A dose omission of >28 days for ibrutinib or lenalidomide is not allowed. If a patient cannot be administered a dose for >28 days due to adverse events or any other reason, the patient should be removed from the study treatment and go to event monitoring.
- g) Patients will be removed from the study if we are unable to manage the adverse events they experience, and it is therefore necessary to permanently discontinue ibrutinib or lenalidomide. These events are listed in the tables in Section 8.3 and 8.5.

8.2 Dose Reductions for Phase I cycles 2 and beyond and Phase II portion (based on Adverse Events in Tables below):

8.21 The following recommended dose modifications will be utilized for ibrutinib, lenalidomide and/or dexamethasone separately as per the best judgment of which drug was most likely to have caused the toxicity:

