### **8.51 Dose Modification for Hepatic Impaired Subjects**

Ibrutinib is metabolized in the liver and therefore subjects with clinically significant hepatic impairment at the time of screening (Child- Pugh class B or C) are excluded from study participation. For subjects who develop mild liver impairment while on study (Child-Pugh class A), the recommended dose reduction for ibrutinib is to a level of 280 mg daily (two capsules). For subjects who develop moderate liver impairment while on study (Child-Pugh class B), the recommended dose reduction is to a level of 140 mg daily (one capsule). Subjects who develop severe hepatic impairment (Child-Pugh class C) must omit ibrutinib until resolved to moderate impairment (Child-Pugh class B) or better. Monitor subjects for signs of toxicity and follow dose modification guidance as needed (Refer to [Appendix XII](#)).

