d) Elimination – The excretion of ibrutinib is predominantly via the feces with approximately 80% recovered mostly within 2 days, whereas ~8% is excreted in urine. Approximately 1% of the ibrutinib is recovered as unchanged drug, all in feces. The half-life elimination is 4-6 hours. Overall, these PK characteristics resulted in minimal accumulation of both parent compound and metabolite PCI-45227 on repeated daily dosing of ibrutinib.

e) Special populations: a small increase in bioavailability was estimated with increasing age. Exposure is predicted to increase approximately 14% and decrease approximately 20% in subjects of 81 and 49 years of age, compared to a typical 67-year old subject. No statistically significant

effects were observed for the other covariates tested, i.e., sex, race, mild and moderate renal impairment, mild hepatic impairment and B-cell histology. The recommended doses for patients with mild and moderate liver impairment are 280 mg/day and 140 mg/day (Child-Pugh Class A and B, respectively). It is not recommended to administer ibrutinib to subjects with severe hepatic impairment (Child-Pugh Class C). Pediatric studies are still ongoing.

**15.16 Potential Drug Interactions:** Ibrutinib is primarily metabolized by cytochrome P450 enzyme 3A4/5. Voriconazole and posaconazole can be used concomitantly with ibrutinib as per the dosing guidance described in the specific clinical study protocol. All other strong inhibitors of CYP3A (eg, ketoconazole, indinavir, nelfinavir, ritonavir, saquinavir, clarithromycin, telithromycin, itraconazole, nefazodone, and cobicistat) should be avoided, and an alternative with less CYP3A inhibitory potential should be considered. If the benefit outweighs the risk and a strong CYP3A inhibitor must be used, see the recommended dose modifications described in the specific clinical study protocol.

If a moderate CYP3A inhibitor (eg, fluconazole, erythromycin, amprenavir, aprepitant, atazanavir, ciprofloxacin, crizotinib, diltiazem, fosamprenavir, imatinib, verapamil, amiodarone, dronedarone) is indicated in patients with B-cell malignancies, reduce the ibrutinib dose to 280 mg for the duration of the inhibitor use or as per recommended dose modifications described in the specific clinical study protocol. No ibrutinib dose modifications for moderate inhibitors are required in patients with cGVHD dosed with ibrutinib 420 mg.

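### Phase II admits patients with clinically significant Child-Pugh A impairment, but the dosing sections do not give them the 280 mg/day ibrutinib that the drug information recommends

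*Combined protocol and SAP*

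**What the plan says.** Five places in the protocol bear on this point.

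- **3.29e1 (Phase I exclusion):** "Any currently active, clinically significant hepatic impairment (Child-Pugh class A, B, or C according to the Child Pugh classification".
- **3.29e2 (Phase II exclusion):** "Currently active, clinically significant hepatic impairment Child-Pugh class B or C according to the Child Pugh classification". Class A is not listed.
- **7.12 (Phase II treatment):** "All patients will start with ibrutinib at the dose level determined by the phase I portion". Neither this text nor the 7.12 tables make a hepatic exception; the only footnoted starting-dose change is dexamethasone by age.
- **8.51 (hepatic dose modification):** it says that "subjects with clinically significant hepatic impairment at the time of screening" are excluded, naming only classes B and C. It then provides that for those who "develop mild liver impairment while on study (Child-Pugh class A), the recommended dose reduction for ibrutinib is to a level of 280 mg" daily. It says nothing about class A already present at entry.
- **15.15e (special populations):** "The recommended doses for patients with mild and moderate liver impairment are 280 mg/day and 140 mg/day" for Child-Pugh A and B respectively, with no condition on when the impairment arose. Just before this, the same paragraph reports that no statistically significant "effects were observed for the other covariates tested, i.e., sex, race, mild and moderate renal impairment, mild hepatic impairment and B-cell histology".

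**The concern.** The eligibility rule was deliberately split by phase, and the Phase II half lets in a group that Phase I kept out. The protocol already has a recommended ibrutinib dose for that group, but only in the pharmacokinetic part of the drug information. Neither section that a site would use to set the dose (7.12 for the start, 8.51 for hepatic adjustment) carries it over or points to it.

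The result is uneven. A patient whose class A impairment appears on study is brought down to 280 mg. A patient who arrives with it starts, under 7.12, at the full Phase II dose. That dose was chosen in a cohort from which such patients were excluded, so Phase I gives no tolerability data for them. What is at stake is overdosing, relative to the protocol's own recommendation, in a small number of patients. No statistical operating characteristic is involved.

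**Working it through.** **1. Who is affected.** Appendix XII defines class A as 5 to 6 points, and the minimum score is 5.

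- Normal liver: five items at 1 point each = 5, class A.
- Albumin of 28–35 g/L only: 2 + (4 × 1) = 6, class A.

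The laboratory criteria in 3.17 limit bilirubin, AST/ALT and PT/INR but set no limit on albumin, so a score of 6 remains possible whatever the local normal ranges. The score alone therefore does not mark out the affected group; the words *clinically significant* do, and the protocol does not define them. Known hepatitis B or C below a viral-load limit is also allowed (3.29g), so an affected patient is plausible. The protocol gives no expected number.

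**2. Starting dose for such a patient, by section.**

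| Section | Class A at entry | Class A developing on study |
|---|---|---|
| 7.12 | Phase I dose | not addressed |
| 8.51 | not addressed | 280 mg/day |
| 15.15e | 280 mg/day | 280 mg/day |

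The first column is where 7.12 and 15.15e disagree.

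**3. Size of the disagreement.** The chosen Phase II dose is not in the documents, so every level in 7.31 is shown. Ratio = Phase II dose ÷ 280 mg. Reduction steps are those left before discontinuation in Table 8.223.

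| Phase II dose | Ratio to 280 mg | Reduction steps available |
|---|---|---|
| 280 mg | 280/280 = 1.0 | 0 |
| 420 mg | 420/280 = 1.5 | 1 |
| 560 mg | 560/280 = 2.0 | 2 |
| 700 mg | 700/280 = 2.5 | 3 |
| 840 mg | 840/280 = 3.0 | 4 |

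The recommendation is exceeded at every level except −1. These are ratios of dose; they do not estimate exposure or toxicity.

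**4. Share of the sample.** Each affected patient is 1/34 = 2.9% of the evaluable Phase II patients. This is a weight per patient, not a prevalence estimate.

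**The case against.** The strongest reply is that 7.12 is a general sentence that the protocol itself does not apply literally. It also gives dexamethasone as 40 mg for everyone while a footnote lowers it for patients aged 75 or over. Lenalidomide is adjusted for renal function in Table 8.32, and ibrutinib is lowered for CYP3A inhibitors in 15.19b, neither of which the Phase II text mentions. On that pattern 15.15e simply supplies the special-population dose, and all that is missing is a cross-reference. This stands in part: a site could reasonably apply 15.15e. It does not settle the matter. Section 7 does mark starting-dose exceptions when it wants them (dexamethasone by age, and in 7.11 lenalidomide by renal function). The section written for hepatic dosing is silent on class A at entry.

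A second reply is that 8.51 can be read as treating only B and C as clinically significant. But 3.29e1 uses the same term for class A, so at best the text is ambiguous.

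Third, 15.15e found no significant covariate effect of mild hepatic impairment, and 280 mg is a recommendation, not a limit. Both are true. Yet the same paragraph goes on to recommend 280 mg, and 8.51 adopts it for impairment arising on study, so the protocol has already made its choice.

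Fourth, there are safeguards: FDA review before Phase II, no lenalidomide in Cycle 1, blood chemistries every two weeks for the first two cycles, toxicity monitoring under 8.51 and the Grade 4 or higher stopping rule. They limit the harm, but none of them sets a starting dose.

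**Conclusion.** The concern holds, as a minor one. For a Phase II patient who enters with clinically significant Child-Pugh A impairment, 7.12 and 15.15e lead to different ibrutinib starting doses, and nothing in the protocol says which takes precedence. Following 7.12 gives 1.5 to 3.0 times the recommended dose if Phase II runs at 420 to 840 mg, and no excess if it runs at 280 mg.

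The conclusion rests on reading 3.29e2 as admitting clinically significant class A, which is the plain sense when it is set beside 3.29e1. It makes no assumption about how many such patients will enroll; the number is probably small and may be zero. It does not claim a demonstrated rise in exposure or toxicity.

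**What to change.** **Preferred change.** Add an exception to 7.12, in the form 7.11 already uses for renal dysfunction: a patient with active, clinically significant Child-Pugh A impairment at entry starts ibrutinib at 280 mg daily, or at the Phase II dose if that is lower. Have 8.51 cite 15.15e. Key the rule to clinically significant impairment, with the investigator's judgement recorded at entry. Keying it to the score alone would catch every patient with a normal liver.

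**Alternative.** Exclude clinically significant class A from Phase II as well, matching 3.29e1. This costs a few otherwise eligible patients.

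**Cost of the preferred change.** One sentence and one cross-reference in an amendment; bilirubin, albumin and INR are already collected. A few patients would receive less than the Phase II dose and still count in the primary endpoint. They would also have no adverse-event reduction step in Table 8.223, so a first required reduction means stopping ibrutinib, and 8.1d then applies: "If either ibrutinib or lenalidomide must be permanently discontinued, the patient will be removed from the protocol therapy". Section 8.5 likewise sends patients with a listed adverse event at the lowest dose to event monitoring. Because 8.51 already uses 140 mg for class B developing on study, the amendment should also say whether 140 mg is open to these patients as an adverse-event reduction.
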